### PROTOCOL AMENDMENT 1 SUMMARY OF CHANGES

Change	Location	Rationale
Changed Medical Monitor name and contact information	Page 2	Change in personnel.
Clarified permitted and prohibited treatments for acne vulgaris on the trunk	Section 7.2	Since subjects originating in DRM01B-ACN03 are allowed, if warranted by the Investigator, to use study drug on the trunk, these subjects are not allowed to use any concomitant medication to treat acne vulgaris in the DRM01B-ACN05 study. Subjects originating in DRM01B-ACN04 are not allowed to use study drug on the trunk, and therefore, may use approved topical acne treatments on the trunk in the DRM01B-ACN05 study.

**PROTOCOL SYNOPSIS**

Title:	An Open-Label Study Assessing Long-Term Safety of Olumacostat Glasaretil Gel in Subjects with Acne Vulgaris
Protocol Number:	DRM01B-ACN05
Phase:	3
Number of Sites:	Approximately 100
Study Population	Subjects who participated in either the DRM01B-ACN03 or DRM01B-ACN04 studies
Sample Size	Approximately 700
Study Treatment	Olumacostat Glasaretil Gel, 5.0%, applied twice daily
Study Objective:	To assess the long term safety of Olumacostat Glasaretil Gel, 5.0% in subjects with acne vulgaris
Duration of Subject Participation:	Up to 36 weeks
Study Visit Schedule	Day 1 (Week 12 visit of DRM01B-ACN03 or DRM01B-ACN04), Weeks 2 (phone call only), 4, 8, 12, 16, 20, 24, 28, 32, 36 (Study Exit)

Study Design/Summary:
 
This is an open label, long-term safety study enrolling approximately 700 subjects who participated in either the DRM01B-ACN03 or DRM01B-ANC04 studies. All subjects will sign an informed consent (adults)/assent (children) prior to continuing in this open label study.
 
Eligible subjects will receive open label treatment with Olumacostat Glasaretil Gel, 5.0% and continue to dose twice daily for up to 36 weeks. Study drug will be applied twice daily to the face. Subjects, who participated in DRM01-ACN03 study with acne on the chest, back or shoulders and applied study drug to affected areas will be allowed to continue to apply study drug to the affected areas. Subjects who participated in DRM01-ACN04 study will continue to apply study drug to the face only. Subjects will return to the clinic at Weeks 4, 8, 12, 16, 20, 24, 28, 32, and 36 (Study Exit). A follow-up phone call at Week 2 will be made to assess safety (adverse events) only.
 
At the Week 12 and 24 visits, if the severity of acne has become worse, the subject should be withdrawn, at the investigator's discretion. Severity of acne will be assessed by IGA and limited to the face only.
 
Efficacy will be assessed through investigator global assessment of acne (IGA).
 
Safety will be assessed through adverse events, local skin reactions (LSRs), serum chemistry, hematology and urinalysis laboratory testing, physical examination, ECGs, pulse and blood pressure.
 
Photographs of the face will be taken for all subjects at a subset of study sites in order to visually assess the appearance of acne vulgaris during the course of the study.
 
During clinic visits, subjects will be asked to complete the Acne Patient Self-Questionnaire.
	

## **1 INTRODUCTION**

### **1.1 Product Development Rationale**

Acne arises from a combination of physiological changes in the skin including altered sebaceous gland cell differentiation, heightened sebum production, localized bacterial colonization and inflammation. Although acne is generally viewed as a benign dermatological disease of adolescence, more severe forms may lead to permanent scar formation, with some of these patients suffering from psychological injury and significant loss of self-worth. Recent scientific advances in the understanding of the complex multi-factorial nature of this common disease offer great opportunity for scientific innovation through selective targeting of key elements of the disease process.

Sebum is a waxy/oily substance comprised of cholesterol, fatty acids, fatty alcohols, triglycerides (TGs), wax esters, sterol esters and squalene produced by sebaceous gland cells [1]. Sebaceous glands are associated with hair follicles. The basal layer of sebocytes just inside the basement membrane consists of small, nucleated cells devoid of lipid droplets. This layer contains the dividing cells that replenish the gland as cells are lost in the process of holocrine rupture. As cells move from the basal layer towards the center of the gland, they differentiate and produce lipids that accumulate in droplets. Eventually the cells become distended with lipid droplets and the nuclei and other sub-cellular structures disappear. As the cells approach the sebaceous duct, they disintegrate and release their contents through holocrine secretion. In acne, diglycerides and free fatty acid levels may be increased by bacterial degradation of diglycerides and triglycerides present within sebum. Free fatty acids may promote inflammatory response in acne by activating local immune cells and their subsequent release of pro-inflammatory factors.

A direct correlation between the degree of acne improvement and the extent of sebum reduction produced by different oral anti-acne medications has been established [2]. The oral retinoid 13-cis-retinoic acid (13-cis-RA, Accutane®) is particularly effective at reducing sebum output although its mode-of-action is not likely related to a direct effect on sebum synthesis pathways [3].

Topical agents routinely prescribed for acne, including antibiotics, retinoids and combinations thereof, often produce only modest therapeutic benefits and do not affect sebum production. A locally-delivered medication that selectively inhibited sebum formation would represent a breakthrough advance in reducing the pathogenic influences of sebum overproduction in acne.

Acetyl-coenzyme A carboxylases (ACCs) have crucial roles in fatty acid metabolism in humans and most other living organisms [4]. ACC catalyzes the carboxylation of acetyl-CoA to form malonyl-CoA. This is the first committed step in fatty acid biosynthesis and is the rate limiting reaction for the pathway [5, 6, 7]. These fatty acids then can be stored or converted to triglycerides (TGs) and phospholipids. In addition to its role as a substrate in fatty acid biosynthesis, malonyl-CoA, also plays an important regulatory role in controlling mitochondrial fatty acid uptake through allosteric inhibition of carnitine palmitoyltransferase I (CPT-I), the enzyme catalyzing the first committed step in mitochondrial fatty acid oxidation [8]. Malonyl-CoA, therefore, is a key metabolic signal for the control of fatty acid production and utilization in response to dietary changes and altered nutritional requirements in animals [6]. As a result of

its unique position in intermediary metabolism, inhibition of ACC offers the ability to inhibit *de novo* fatty acid production in lipogenic tissues, such as liver, adipose tissue, and sebaceous glands.

A variety of structurally diverse ACC inhibitors has recently been described in the scientific and patent literature for potential use in metabolic syndrome. One class of ACC inhibitors, including TOFA (5-(tetradecyloxy)-2-furancarboxylic acid), consists of lipophilic fatty acid mimetics that compete with acetyl-CoA in the ACC-mediated formation of malonyl-CoA. Investigators have demonstrated that TOFA reduced fatty acid synthesis and TG secretion both in cultured hepatic cells [8, 10] and in experimental animals [11, 12], reduced plasma cholesterol and TGs in experimental animals including rhesus monkeys [10, 11], and reduced body weight [13].

The ability to deliver TOFA topically could offer a means to inhibit *de novo* fatty acid production in sebaceous glands, introducing a new treatment paradigm for acne vulgaris.

## 1.2 Summary of Investigational Program

Dermira, Inc. is pursuing the development of olumacostat glasaretil, previously referred to as DRM01B, a pro-drug of TOFA, sarcosine ester, a topical treatment for acne vulgaris. Olumacostat glasaretil is hydrolyzed by esterases *in vivo* to form the pharmacologically active moiety, TOFA. TOFA is converted to Tofyl-CoA intracellularly, which competes with acetyl-CoA in the ACC-mediated formation of malonyl-CoA. As a result, inhibition of malonyl-CoA synthesis offers a means to inhibit *de novo* fatty acid production in the sebaceous glands in subjects with acne vulgaris. Olumacostat glasaretil is a new chemical entity and has been formulated for clinical development as Olumacostat Glasaretil Gel, 5.0%.

A summary of clinical and nonclinical pharmacology, toxicology and metabolism data is presented below. Detailed information is provided in the current Investigator's Brochure.

Safety pharmacology studies were conducted with olumacostat glasaretil administered intravenously (IV) which included neurobehavioral and pulmonary function studies in rats and a cardiovascular study in telemetered minipigs. These studies revealed no adverse findings attributable to olumacostat glasaretil. *In vitro* studies assessing the effects of olumacostat glasaretil and TOFA upon human ether-à-go-go-related gene (hERG) ionic conductance in human embryonic kidney (HEK) cells also revealed no significant inhibition at the maximum concentrations tested. Overall, the results from the safety pharmacology showed no adverse effects at exposures to parent drug and/or TOFA several orders of magnitude beyond that anticipated to be seen following topical application in humans.

Following IV administration in rats and minipigs, olumacostat glasaretil was quickly metabolized to TOFA; no evidence of any gender-specific differences or accumulation upon repeated dosing of either olumacostat glasaretil or TOFA was observed. With oral administration in rats, low ng/mL levels of olumacostat glasaretil were noted while exposure to TOFA reached levels exceeding 1 µg/mL. *In vitro* metabolism and plasma protein binding experiments indicated that olumacostat glasaretil was metabolized and bound to plasma protein in a similar manner between humans and the species utilized for toxicology and safety pharmacology assessments (rat and minipig).

Toxicokinetic assessments conducted following the topical dermal application of Olumacostat Glasaretil Gel to minipigs indicated that olumacostat glasaretil and TOFA were poorly absorbed; peak plasma levels recorded in these studies were below the detectable limit for olumacostat glasaretil and while TOFA was detectable following application of the highest strength of Olumacostat Glasaretil Gel (7.5% w/w), mean values did not exceed 6 ng/mL for TOFA. The test article used in this study is the same formulation and concentration that was used in the clinical proof of concept study (DR01B-ACN01) and the same formulation that was included in the clinical dose ranging trial DR01B-ACN02).

Toxicology studies conducted with olumacostat glasaretil included dermal studies in minipigs of up to 13 weeks in duration, IV studies in rats and minipigs of up to 4 weeks in duration, and oral studies in rats of up to 90 days in duration. Based upon the nonclinical studies conducted to date, olumacostat glasaretil has exhibited an acceptable safety profile. No test article-related effects were noted in any nonclinical study, aside from histological findings associated with the non-glandular stomach (fore-stomach) in the 13-week rat oral study. This finding was considered a direct local effect (not due to systemic absorption), reversible and non-adverse, and is of doubtful clinical relevance given the absence of this structure in humans. In the other toxicology studies, there were no remarkable olumacostat glasaretil-related findings and olumacostat glasaretil was well tolerated. No adverse systemic effects were associated with mean peak plasma exposures to olumacostat glasaretil and TOFA up to 9955 and 3630 ng/mL, respectively, which are concentrations exceeding 4000-fold that seen following the dermal application of maximum feasible doses (10 mg/kg) to minipigs. In vivo and in vitro studies conducted to assess dermal sensitization, ocular irritation, and phototoxicity did not reveal any remarkable effects following the exposure of cells/tissues to olumacostat glasaretil. Genetic toxicology results indicated that olumacostat glasaretil was neither mutagenic nor clastogenic. Predictive software assessments indicated there were no potential theoretical manufacturing impurities or metabolic products that were of mutagenic concern. Overall, the results of the nonclinical toxicology and safety pharmacology studies suggest the safety risks posed by olumacostat glasaretil are low.

Two clinical studies, DRM01B-ACN01 and DRM01B-ACN02, have been completed as part of the Phase 2 development program. DRM01B-ACN01 was a proof of concept study which assessed the safety and efficacy of one strength of Olumacostat Glasaretil Gel compared to vehicle gel in adult subjects with acne vulgaris. DRM01B-ACN02 was a dose-ranging study which assessed the safety and efficacy of multiple strengths and regimens of Olumacostat Glasaretil Gel and vehicle gel in adult subjects with acne vulgaris. In both studies, Olumacostat Glasaretil Gel was shown to be well-tolerated and demonstrated statistically significant improvements in acne lesions counts and severity. Additional information on these studies is provided below.

### **Study DRM01B-ACN01**

DRM01B-ACN01 was randomized, vehicle controlled, parallel group study designed to assess the safety and tolerability of Olumacostat Glasaretil Gel, 7.5% in healthy volunteers (Phase 1) before assessing the safety, tolerability and preliminary efficacy of the drug in subjects with acne vulgaris (Phase 2a). In the Phase 1 portion of the study, 6 healthy volunteers applied study Olumacostat Glasaretil Gel twice daily, to the face, for one week. Review of the data from Phase

1 showed that Olumacostat Glasaretil Gel was well tolerated with no safety concerns. As such, the Phase 2a portion of the study was conducted.

In the Phase 2a portion of the study, Olumacostat Glasaretil Gel was applied, twice daily, to the face in 108 adult subjects with acne vulgaris for a 12-week treatment period. Similar to Phase 1, Olumacostat Glasaretil Gel was well tolerated with most AEs reported to be mild to moderate severity. Subjects treated with Olumacostat Glasaretil Gel had significantly greater reductions in inflammatory and noninflammatory lesion counts from Baseline to Week 12 compared with subjects treated with vehicle gel. In addition, a significantly greater proportion of subjects treated with Olumacostat Glasaretil Gel had a successful improvement in IGA score (corresponding to less severe acne) than subjects treated with vehicle gel.

### **Study DRM01B-ACN02**

Study DRM01B-ACN02 was a Phase 2 dose-ranging study in adult subjects with acne vulgaris on the face. The study was a randomized, vehicle controlled, parallel group study designed to assess the efficacy and safety of Olumacostat Glasaretil Gel at a doses of 7.5% BID, 7.5% QD, and 4.0% QD, compared to vehicle BID or QD in subjects with moderate to severe facial acne.

A total of 420 adult subjects were randomized to active and vehicle in a 2:2:2:1:1 fashion. Study treatments continued for 12 weeks. Subjects returned to the study clinic at Weeks 1, 2 (phone call only), 4, 8 and 12 (study exit).

The results of the study showed that all three Olumacostat Glasaretil Gel treatment groups showed statistically significantly greater reductions in the absolute change in inflammatory lesion counts from baseline to Week 12 than the combined vehicle group. The LS mean changes in inflammatory lesion counts were -14.6 and -14.5, and -15.0 for the Olumacostat Glasaretil Gel, 4.0% QD, 7.5% QD, and 7.5% BID groups, respectively, compared with -10.7 for the combined vehicle group ( $P = 0.011$ ,  $P = 0.014$ , and  $P = 0.011$ , respectively).

All 3 Olumacostat Glasaretil Gel treatment groups showed statistically significantly greater reductions in the absolute change in noninflammatory lesion counts from baseline to Week 12 than the combined vehicle group. The LS mean changes in noninflammatory lesion counts at Week 12 were -15.3, -13.4, and -17.5 for the Olumacostat Glasaretil Gel 4.0% QD, 7.5% QD, and 7.5% BID groups, respectively, compared with -9.3 for the combined vehicle group ( $P = 0.004$ ,  $P = 0.050$ , and  $P < 0.011$ , respectively).

The Olumacostat Glasaretil Gel 4.0% QD and 7.5% BID groups each had a statistically significantly greater proportion of subjects achieve a minimum 2-grade improvement (reduction) in IGA score from baseline at Week 12 compared with the combined vehicle group. The percent of subjects achieving this endpoint was 21.6% in the Olumacostat Glasaretil Gel 4.0% QD and 25.9% of subjects in the Olumacostat Glasaretil Gel 7.5% BID group compared with 9.8% in the combined vehicle QD group ( $P = 0.024$  and  $P = 0.004$ , respectively).

A comparison of subjects with a 2-grade improvement in IGA score with or without a concurrent IGA score of clear or almost clear at Weeks 4, 8, and 12 showed that in each treatment group at each IGA assessment time point, most subjects who achieved a 2-grade improvement in IGA score also had an IGA score of clear or almost clear.

Pharmacokinetic (PK) results, assessed in a subset of subjects, showed that plasma concentrations of olumacostat glasaretil on Day 1 were undetectable for all but one subject, who had a plasma concentration of 0.304 ng/mL at one time point (2 hours post-dosing). Plasma concentrations of olumacostat glasaretil at Week 8 were undetectable for all tested subjects. Plasma concentrations of TOFA on Day 1 were undetectable in most subjects, but detectable in a few subjects in each dose group, with values ranging from 0.101 to 1.02 ng/mL. Plasma concentration of TOFA at Week 8 were undetectable for most subjects in the Olumacostat Glasaretil Gel QD dose groups, but detectable in a few subjects, with values ranging from 0.100 to 0.299 ng/mL. In the Olumacostat Glasaretil Gel, 7.5% BID group, approximately half of the tested subjects had detectable TOFA levels at each time point, with mean values ranging from 0.156 to 0.340 ng/mL.

The most common AEs reported during the study were nasopharyngitis, upper respiratory tract infection, and application site pruritus. Most AEs were mild or moderate in severity. Erythema was the most common LSR. Laboratory values, vital signs, and ECGs measured at the end of the study were generally consistent with baseline values, with no clinically significant trends.

### **Study Rationale**

Data from the completed Phase 2 dose ranging study, DRM01B-ACN02, and data from study DRM01B-ACN01 have shown that Olumacostat Glasaretil Gel was well tolerated at multiple concentrations. Olumacostat Glasaretil Gel at a strength of 5.0% has been selected as the concentration to take forward in Phase 3 development. Two Phase 3 pivotal trials, DRM01B-ACN03 and DRM01B-ACN04, are planned as part of the Phase 3 development program and will include adults and children (ages 9 years and older) in order to assess the safety and efficacy of Olumacostat Glasaretil Gel for the treatment of acne vulgaris.

The DRM01B-ACN05 study described herein is an open-label study to assess the long term safety of continuous treatment with Olumacostat Glasaretil Gel, 5% for up to an additional 36-weeks in subjects who have completed either of the DRM01-ACN03 or DRM01-ACN04 studies.

### **1.3 Study Conduct Statement**

This study will be conducted in compliance with the protocol, according to current United States federal regulations (Title 21, Code of Federal Regulations [CFR] Parts 11, 50, 54, 56, 312, and 314 as appropriate) and the principles of the International Conference on Harmonisation (ICH) (ICH E6 1997) Good Clinical Practice (GCP), Food and Drug Administration (FDA) guidelines, Canadian guidelines and the Declaration of Helsinki, 1964 (as amended in Edinburgh [2000]).

## **2 STUDY SUMMARY**

This study is an open-label, long-term safety study enrolling approximately 700 subjects who participated in either DRM01B-ACN03 or DRM01B-ACN04 studies. All subjects will sign an informed consent / assent prior to continuing in this open label study.

Eligible subjects will receive open label treatment with Olumacostat Glasaretil Gel, 5.0% and continue to dose twice daily for 36 weeks. Subjects, who participated in DRM01-ACN03 study with acne on the chest, back or shoulders and applied study drug to affected areas will be allowed to continue to apply study drug to the affected areas. Subjects who participated in DRM01-ACN04 study will continue to apply study drug to the face only. Subjects will receive a phone call at Week 2 to assess safety, and will return to the clinic at Weeks 4, 8, 12, 16, 20, 24, 28, 32, and 36 (End of Study).

Efficacy will be assessed via a static evaluation of qualitative overall acne severity, the investigator's global assessment of acne (IGA).

At the Week 12 and 24 visit, if the severity of acne has become worse, as determined by the IGA, the subject should be withdrawn, at the investigator's discretion. Severity of acne will be assessed on the face only.

Safety will be assessed through adverse events, local skin reactions (LSRs), serum chemistry, hematology and urinalysis laboratory testing, ECGs, physical examination, pulse and blood pressure.

Photographs of the face will be taken for all subjects in a subset of study sites in order to assess visually, the appearance of acne vulgaris during the course of the study.

During the clinic visit, subjects will be asked to complete the Acne Patient Self-Questionnaire.

### **3 STUDY OBJECTIVES**

The objective of this study is to assess the long-term safety of Olumacostat Glasaretil Gel, 5.0%, in subjects with acne vulgaris.

This study may be stopped once at least 100 subjects have been treated for 36 weeks.

### **4 STUDY ENDPOINTS**

No inferential statistics are planned for this study.

### **5 STUDY DESIGN**

#### **5.1 Duration of the Study**

Each subject will participate in this study for up to 36 weeks.

#### **5.2 Study Population and Number of Subjects**

Approximately 700 subjects who participated in either of the DRM01B-ACN03 or DRM01B-ACN04 studies may enroll in this trial.

### **5.3 Selection of Subjects**

Subject selection criteria are outlined below. Any questions on the eligibility of a subject for this study must be referred to the Sponsor or its designee, prior to enrollment. No exceptions to inclusion or exclusion criteria will be made.

#### **5.3.1 Inclusion Criteria**

Subjects must meet all of the following criteria to be eligible for study participation:

1. Signed informed consent or assent (for subjects under legal adult age)
2. Completed Week 12 visit of either DRM01B-ACN03 or DRM01B-ACN04 studies.
3. Willing to comply with the protocol. Subjects under legal adult age will be assessed by the investigator as to their ability to comply with the protocol
4. Willing to refrain from using any treatments on the face for acne vulgaris, other than the investigational product, including topical or systemic antibiotics.

#### **5.3.2 Exclusion Criteria**

Subjects meeting any of the following criteria are not eligible for study participation:

1. Abnormal clinically significant findings on physical exam, vital signs or ECG at Week 12 visit of either the DRM01-ACN03 or DMR01-ACN04 studies that would make further treatment with Olumacostat Glasaretil Gel contraindicated, as determined by the Investigator
2. Any other condition which, in the judgment of the investigator, would put the subject at unacceptable risk for participation in the study

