## **8 STUDY PROCEDURES**

The procedures required for subject evaluation at each study visit are outlined below and in the study Schedule of Visits and Procedures (see [Appendix 1](#)). The timing of each study day is relative to the day of initial dosing (Baseline/Day 1). Visit windows are provided to allow study sites some flexibility in maintaining the study visit schedule for participating subjects. Out of window visits may be unavoidable in certain circumstances. Out of window visits are not considered deviations to the protocol.

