### **8.1 Day 1 (Week 12 Visit of DRM01B-ACN03 or DRM01B-ACN04 Study)**

- Obtain written informed consent/assent. For subjects under legal adult age, both parents or legal representatives may be required to sign informed consent as applicable.
- Assess Inclusion/Exclusion criteria
- Dispense study drug and diary
- Schedule next visit

The following Week 12 data collected as part of the DRM01-ACN03 or DRM01-ACN04 study will be used for the Day 1 visit:

- Query subject for concomitant medication use
- Perform a complete physical examination
- Record weight
- Measure pulse and blood pressure
- Collect a 12-lead ECG
- Conduct Investigator Global Assessment
- Collect Acne Patient Self-Questionnaire
- Draw blood samples for laboratory tests and urine for urinalysis. Include serum pregnancy test for women of childbearing potential
- Assess Local Skin Reactions (LSR)
- Review and record AEs
- Collect photographs (selected sites)

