### **9.4.4 Laboratory Evaluations**

Laboratory tests will be collected to evaluate safety in all study subjects and analyzed using a central laboratory. Labs will be collected per the Schedule of Visits and Procedures (see [Appendix 1](#)) or more frequently as clinically indicated. Laboratory samples are to be shipped on the same day as collected. No more than 4 mL/kg total will be collected over an 8-week period in subjects under legal adult age. Laboratory tests are described below.

Hematology: hematocrit, hemoglobin, red blood cell (RBC) count, white blood cell count and differential (%), mean corpuscular hemoglobin (MCH), mean corpuscular hemoglobin concentration (MCHC), mean corpuscular volume, RBC morphology, platelet count, absolute

neutrophils, absolute lymphocytes, absolute monocytes, absolute eosinophils, and absolute basophils.

Chemistry: sodium, potassium, chloride, calcium, phosphorus, bicarbonate, uric acid, blood urea nitrogen (BUN), creatinine, total protein, albumin, aspartate aminotransferase (AST), alanine aminotransferase (ALT), alkaline phosphatase, bilirubin (total and direct), and glucose (fasting or non-fasting).

Serum pregnancy testing will be performed at Baseline/Day 1 and Week 36 Study Exit or Early Termination visits. Urine pregnancy testing (beta human chorionic gonadotropin [ $\beta$ -hCG]) will be performed at Weeks 4 – 36 visits for all females unless post-menopausal/sterile.

Urinalysis: pH, specific gravity, protein, glucose, ketones, bilirubin, blood, nitrite, urobilinogen, leukocyte esterase. A microscopic examination of urine will be performed if clinically indicated (e.g. a positive dipstick for protein, blood, leukocyte esterase) in the opinion of the Investigator based on the findings of the urinalysis or clinical signs and symptoms. Any new or worsened clinically significant laboratory result is to be recorded as an AE after study drug dosing.

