The central laboratory should be used for any laboratory testing required for a subject during study participation, including laboratory testing needed for unscheduled visits. If an immediate result is required to adequately care for a subject, a duplicate sample may be submitted to a local lab. Clinically significant laboratory results must be recorded as an AE, preferably as a diagnosis rather than individual test results. Any subject who has a clinically significant laboratory test result will be evaluated by the Investigator, and will be treated and/or followed up until the value returns to clinically acceptable levels, in the opinion of the investigator.

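### ACN05 names no pregnancy exclusion and does not tie Day 1 dispensing to a known pregnancy result, a small gap unless the parent Week 12 visit already includes a same-day test

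*Protocol*

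**What the plan says.** **Eligibility.** Protocol 5.3.1 has four inclusion criteria: consent or assent, a completed parent Week 12 visit, willingness to comply, and no other facial acne treatment. Protocol 5.3.2 has two exclusions. The first covers clinically significant findings on physical exam, vital signs or ECG. The second is open-ended: "Any other condition which, in the judgment of the investigator, would put the subject at unacceptable risk for participation in the study". Pregnancy appears in neither list.

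**Day 1.** Protocol 8.1 lists "Dispense study drug and diary" among the Day 1 tasks, with no condition attached. Among the parent-study Week 12 data that serve as Day 1 data, it lists "Draw blood samples for laboratory tests and urine for urinalysis" and adds "Include serum pregnancy test for women of childbearing potential". Section 8 treats Day 1 as the day of initial dosing. Section 9.1 says that procedures are carried over from the parent visit and not repeated. Its carry-over list includes pregnancy testing without giving the specimen type.

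**Laboratory rules.** Protocol 9.4.4 has laboratory tests analysed centrally and states: "Laboratory samples are to be shipped on the same day as collected". On timing it says: "Serum pregnancy testing will be performed at Baseline/Day 1 and Week 36 Study Exit or Early Termination visits". Urine pregnancy testing starts at Week 4, and its Day 1 cell in Appendix 1 is empty. The same section allows an exception: "If an immediate result is required to adequately care for a subject, a duplicate sample may be submitted to a local lab".

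**Pregnancy on study.** Protocol 9.4.11 stops dosing and withdraws a subject who becomes pregnant during participation, with follow-up to at least 4 weeks after delivery.

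**The concern.** The plan treats pregnancy as incompatible with dosing once a subject is in the study, but it does not check entry against that rule. A serum sample shipped to a central laboratory cannot be expected to give a result at the visit where the gel is handed out. A site working from these documents alone could therefore start a pregnant subject on active drug while the result is pending.

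The stake is avoidable fetal exposure, chiefly in subjects who had vehicle in ACN03 or ACN04. For them, ACN05 Day 1 is the first exposure to olumacostat glasaretil. A prior-active subject who is pregnant on Day 1 has probably been exposed already, so a Day 1 check could only shorten that exposure. Nothing in the SAP depends on this point.

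**Working it through.** The plan states no figure on this point, so there is none to reproduce. The check is mainly a comparison of sections.

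**Step 1: could any provision stop dispensing while the result is pending?**

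| Provision | What it acts on | Holds drug until a result is known? |
|---|---|---|
| 5.3.1, four inclusion criteria | Consent, Week 12 visit, compliance, other treatments | No |
| 5.3.2, exclusion 1 | Physical exam, vital signs, ECG | No; laboratory results are not listed |
| 5.3.2, exclusion 2 | A condition the investigator judges an unacceptable risk | No; a pending result is not a known condition |
| 8.1, dispensing | Day 1 visit | No condition stated |
| 9.4.4, serum test | Day 1 sample under central-laboratory rules | No |
| 9.4.4, local duplicate sample | Need for an immediate result in caring for a subject | No; optional |
| 9.4.4 and Appendix 1, urine test | Week 4 onward | No; not scheduled on Day 1 |
| 9.4.11 | Pregnancy arising during participation | No; acts afterwards |

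None does. That the serum pregnancy sample goes to the central laboratory is read from the general rules of 9.4.4, the section that contains the test.

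**Step 2: how many applications could precede the result?** Let d be the days from Day 1 to the central result. The documents give no turnaround, so d = 1 to 3 is an assumption. Dosing is twice daily. SAP 6.8.1 says that one or two doses are expected on the first day, depending on the time of the visit. Assume also that the site acts on the result no later than between the two doses of the day it arrives.

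- Fewest: 1 on Day 1, 2(d − 1) on the days between, 0 on the result day. Total 2d − 1.
- Most: 2 on Day 1, 2(d − 1) on the days between, 1 on the result day. Total 2d + 1.

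| d (assumed) | Fewest | Most |
|---|---|---|
| 1 | 1 | 3 |
| 2 | 3 | 5 |
| 3 | 5 | 7 |

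The range is 1 to 7 applications, and it moves directly with the assumed turnaround.

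**Step 3: a figure that does not measure the problem.** The next scheduled test is Week 4: target day 29 ± 4, so days 25 to 33, which is 24 to 32 days after Day 1. Twice-daily dosing gives 2 × 24 = 48 to 2 × 32 = 64 applications. That interval concerns pregnancies that begin after Day 1. For a pregnancy already present, the Day 1 serum result should arrive well before then.

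**Step 4: how much drug is absorbed?** Protocol 1.2 reports that in ACN02 parent drug was undetectable in all tested subjects at Week 8. With 7.5% twice daily, mean TOFA was 0.156 to 0.340 ng/mL, with about half of the tested subjects detectable. These were adults with facial acne on a higher strength than the 5.0% used here. Under 6.6, subjects from ACN03 may also treat the trunk. The levels suggest low exposure but do not set an upper bound for ACN05.

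**The case against.** The strongest objection is that Day 1 is not governed by these documents alone. It is the exit visit of ACN03 or ACN04, and 8.1 and the Appendix 1 footnote both treat the pregnancy test as parent-study Week 12 data. Section 9.1 lists pregnancy testing separately from laboratory evaluations and does not name the specimen. A same-day test may therefore already be part of that visit. This stands as a limit: the documents neither show such a test nor rule it out. Even if it exists, ACN05 still names no exclusion and does not link the result to dispensing.

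Second, a known pregnancy is already manageable. Exclusion 2 allows the investigator to exclude it, 5.3 sends eligibility questions to the Sponsor before enrollment, and a late positive result would reasonably be handled as 9.4.11 describes. This also stands, and it narrows the gap to the interval between the blood draw and the result.

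Third, the likely harm is small. Absorption is low, and the nonclinical summary in 1.2 reports no adverse systemic effects at plasma exposures exceeding 4000-fold those seen after maximum feasible dermal dosing in minipigs. It also reports no mutagenic or clastogenic signal. That limits the weight of the point. It is not evidence on fetal risk: the summary names no reproductive or developmental study, although the Investigator's Brochure may describe one.

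A reader might infer that ACN05 knowingly admits pregnant subjects, or that sites will dose them unchecked. The documents do not support either reading. A serum test is required on Day 1, the investigator can exclude a known pregnancy, and the parent visit may supply an earlier answer.

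**Conclusion.** The point holds as a gap in ACN05 as written. Pregnancy is not a named exclusion, and dispensing is not tied to a known result. The only Day 1 test specified is a serum sample whose result would be expected after the visit. A subject already pregnant at rollover could therefore begin dosing first, unless the parent Week 12 visit includes a same-day test.

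The size is small. The length of exposure is unknown because no turnaround is stated; 1 to 7 applications is an illustration under an assumed 1 to 3 days. How often it would happen cannot be judged without the parent protocols. It would be tempting to call this a demonstrated safety failure, or to use the 48 to 64 applications before Week 4 as its measure. The first needs the parent protocols, and the second describes pregnancies that begin later. No planned analysis changes. This is a cheap improvement to what sites do on Day 1.

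**What to change.** 1. Add pregnancy to the exclusions in 5.3.2.
2. In 8.1, 9.4.4 and Appendix 1, require a negative on-site urine pregnancy test for women of childbearing potential before study drug is dispensed. Run it on the Day 1 urine already collected for urinalysis, and keep the serum test.
3. If the parent Week 12 visit already includes a same-day test, cite that test as the dispensing gate instead of adding one.

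The cost is a short amendment and one extra urine test per woman of childbearing potential. Urine pregnancy tests are already scheduled from Week 4; the assumption is that one can be read at the site on Day 1. Under item 3 there is no extra test.

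Holding the first dose until the serum result arrives is not recommended. Appendix 1 gives Day 1 no visit window, and section 8 defines Day 1 as the day of initial dosing. A hold would separate dispensing from the date that anchors every later visit, and it would interrupt treatment for prior-active subjects.
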